The Composite Interference Screw (CIS) manufactured by Biomatlante is sterile, resorbable and osteoconductive of synthetic origin. The Composite Interference Screw is in the form of a cannulated screw:

Figure 1: Composite Interference Screw

The Composite Interference Screws are available in different diameters (from 7 to 12 mm), and several different lengths depending on the diameters (from 20 to 35 mm). Different diameters and lengths of implants are available to allow adaptation to the bone site but also to the patient's anatomy.

The design is suitable for easy installation, without tissue damage (self-tapping thread and atraumatic head).

These resorbable fixation systems are intended to be fully absorbed by the body during the process of bone healing.

They consist of:

- a polymer: poly (L-lactic-co-D, L-lactic acid) (PLDLLA)
- calcium phosphate granules (Hydroxyapatite and Béta Tricalcium Phosphate)

The polymer / granule ratio of calcium phosphate used here is 75% / 25%.

V.3. INTENDED USE

The Composite Interference Screw is intended to be used for knee ligament reconstructions.

The claimed performance for the Composite Interference Screw is as follows: fixation of the ligament/graft within the bone tunnel until bone consolidation is complete.

V.4. SURGICAL INDICATION

The Composite Interference Screw is indicated for torn ligaments in the knee.

The Composite Interference Screw is reserved exclusively for adults. The material has not been tested on pregnant or breastfeeding women.

V.5. CHOICE OF TREATMENT IN THE STUDY

Recruited patients will have an indication of ACL reconstruction with a tendon graft from hamstring muscles:

- DLSTG (Double-Louped SemiTendinosus and Gracilis) technique: use of tendon grafts from the Double-Louped SemiTendinosus and Gracilis muscles
- ST4 (SemiTendinous) technique: use of a tendon graft only from the SemiTendinosus muscle.

In the femur, the fixation will be assured by an intraductal system (Endobutton) and the composite interference screw will be used for the tibial fixation only. The indication of treatment (surgical or otherwise) after ACL injury will not be influenced by the study and will be performed according to good clinical practice.

Patients for whom a patellar tendon (BPTB technique also called Kenneth Jones technique) is advised by the surgeon according to good clinical practice will not be included.

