- An important medical event: AE that may not result in death, be life-threatening, or require hospitalization may be considered an SAE when, based upon appropriate medical judgment, they may jeopardize the patient and may require medical or surgical intervention to prevent one of the outcomes listed above.

The Investigator must continue to follow the patient until the SAE has subsided or until the condition becomes chronic in nature, stabilizes (in the case of persistent impairment), or the patient dies.

VI.3.3. CLASSIFICATION OF AN ADVERSE EVENT

VI.3.3.1. Severity of event

The severity of AEs must be assessed by the Investigator according to the following definitions. The term “severity” is used to describe the intensity of a specific event. This has to be distinguished from the term “serious”.

- Mild: Events require minimal or no treatment and do not interfere with the participant’s daily activities
- Moderate: Events result in a low level of inconvenience or concern with the therapeutic measures. Moderate events may cause some interference with functioning.
- Severe: Events interrupt a participant’s usual daily activity and may require systemic drug therapy or other treatment. Severe events are usually potentially life-threatening or incapacitating. Of note, the term “severe” does not necessarily equate to “serious”.

VI.3.3.2. Relationship to study product

The clinician must always determine the relationship between all adverse events and the investigated medical device by the examination and evaluation of the participant on the basis of temporal relationship between the AE and application of the device and his/her clinical judgment. In a clinical trial, the investigated medical device must always be suspected. The degree of certainty about causality will be graded using the categories below:

- Definitely Related: There is clear evidence to suggest a causal relationship, and other possible contributing factors can be ruled out. The clinical event, including an abnormal laboratory test result, occurs in a plausible time relationship to study intervention administration and cannot be explained by concurrent disease or other drugs or chemicals. The response to withdrawal of the study intervention (dechallenge) should be clinically plausible. The event must be pharmacologically or phenomenologically definitive, with use of a satisfactory rechallenge procedure if necessary.

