- Probably Related: There is evidence to suggest a causal relationship, and the influence of other factors is unlikely. The clinical event, including an abnormal laboratory test result, occurs within a reasonable time after administration of the study intervention, is unlikely to be attributed to concurrent disease or other drugs or chemicals, and follows a clinically reasonable response on withdrawal (dechallenge). Rechallenge information is not required to fulfill this definition.
- Potentially Related: There is some evidence to suggest a causal relationship (e.g., the event occurred within a reasonable time after administration of the trial medication). However, other factors may have contributed to the event (e.g., the participant's clinical condition, other concomitant events). Although an AE may rate only as "possibly related" soon after discovery, it can be flagged as requiring more information and later be upgraded to "probably related" or "definitely related", as appropriate.
- Unlikely to be related: A clinical event, including an abnormal laboratory test result, whose temporal relationship to study intervention administration makes a causal relationship improbable (e.g., the event did not occur within a reasonable time after administration of the study intervention) and in which other drugs or chemicals or underlying disease provides plausible explanations (e.g., the participant's clinical condition, other concomitant treatments).
- Not Related: The AE is completely independent of study intervention administration, and/or evidence exists that the event is definitely related to another etiology. There must be an alternative, definitive etiology documented by the clinician

VI.3.3.3. Expected adverse events

The most frequent adverse events expected from Composite Interference Screw observed in patients are:

- Postoperative infection
- Irritation
- Allergy
- Reduced patient mobility
- Pain
- Fever
- Inflammatory reaction

Certain adverse events can be treated with medicines or may require additional surgery.

VI.3.4. ADVERSE EVENTS REPORTING

Complete and accurate data on all AEs experienced for the duration of the reporting period, will be reported in the eCRF.

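### The dechallenge conditions in the two top device-causality grades do not suit a screw that is left in place, so device events tend to be graded too low

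*Protocol*

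**What the plan says.** Protocol section VI.3.3.2 (Relationship to study product) opens by telling the clinician to judge causality from the timing of the event relative to use of the device and from clinical judgement, and adds that the device is always to be suspected. It then defines five grades.

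- *Definitely Related*: "The response to withdrawal of the study intervention (dechallenge) should be clinically plausible". The event must also be definitive on pharmacological or phenomenological grounds, "with use of a satisfactory rechallenge procedure if necessary".
- *Probably Related*: several conditions joined by 'and', the last being that the event "follows a clinically reasonable response on withdrawal (dechallenge"). The definition then waives rechallenge: "Rechallenge information is not required to fulfill this definition". It does not waive dechallenge.
- *Potentially Related*: some evidence of a causal link, qualified by "However, other factors may have contributed to the event". An event in this grade may be revisited: "it can be flagged as requiring more information and later be upgraded to" one of the two grades above.
- *Unlikely to be related* and *Not Related*: these need, respectively, improbable timing together with another plausible explanation, and a documented alternative cause.

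On the device, section V.2 states: "These resorbable fixation systems are intended to be fully absorbed by the body during the process of bone healing". Section V.5 states that "the composite interference screw will be used for the tibial fixation only".

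Section VII.4.4 summarises treatment-emergent events by relationship to study treatment and, separately, by severity according to relationship.

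**The concern.** Dechallenge and rechallenge are concepts for an exposure that can be stopped and restarted. The screw is implanted once and left to resorb. The protocol has no withdrawal or re-exposure step. A grading rule that asks for a response to withdrawal therefore asks for something the investigator normally cannot observe. This is a stated rule that gives the wrong grade when followed, not a detail left for the statistical analysis plan. The grade is assigned by the investigator at data entry, and a later analysis plan cannot restore a grade that was never recorded.

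The stake is the safety description. Safety of the screw is a secondary objective (II.2). Section I.2 says that resorbable screws generate inflammatory reactions that the literature describes but has not quantified, and section VI.3.3.3 lists inflammatory reaction, irritation and allergy among the expected events. For events of this kind, a reader of the report will look at how many were graded probably or definitely related.

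**Working it through.** No arithmetic applies and the plan states no figure to reproduce. The check is to take one event through the definitions as written.

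**Assumed event:** a local inflammatory reaction at the tibial fixation site, with plausible onset after surgery, no other likely cause found, and the screw left in place.

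| Grade | Conditions the event meets | Condition in question | Result on a literal reading |
|---|---|---|---|
| *Definitely Related* | Evidence of a link, other factors excluded, plausible timing | Plausible dechallenge response ('should be'), definitive event, rechallenge only if necessary | Hard to assign: no withdrawal response exists, though the wording is not absolute |
| *Probably Related* | Evidence of a link, reasonable timing, other causes unlikely | Reasonable response on withdrawal, joined by 'and' | Not met |
| *Potentially Related* | Some evidence of a link | Other factors may have contributed | Poor fit: none is likely here |
| *Unlikely to be related* | None | Timing must make causality improbable | Not met |
| *Not Related* | None | Alternative cause must be documented | Not met |

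Four things follow.

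1. No grade fits the event cleanly. *Potentially Related* is the highest grade with no withdrawal condition, so it is the natural place for the event to land.
2. The scale is out of order on this point. The dechallenge condition is firmer in *Probably Related* than in the grade above it, so the higher grade could be open when the lower one is closed.
3. The upgrade route does not solve this, because it leads only into the two grades that contain dechallenge.
4. The lead-in and the definitions disagree. The lead-in names timing and clinical judgement. The two top definitions add a condition of a different kind.

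**Could resorption count as withdrawal?** The protocol gives no resorption time, and the visit schedule in III.3 contains no imaging or other measure of when exposure ends. Gradual resorption therefore cannot serve as an observed dechallenge in this study.

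**Exception.** If the screw is removed at re-operation, a withdrawal response can be seen. Section VI.3.3.3 says some events may need additional surgery but does not mention removal of the screw.

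**The case against.** The strongest reply is that this is drug-template wording in a descriptive secondary classification, and that the rest of the section offsets it. Several parts of that reply stand.

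- *Definitely Related* is not closed. Its dechallenge sentence says 'should be', rechallenge applies only if necessary, and an event can be definitive on phenomenological grounds without any withdrawal.
- The section leans against dismissing a device link. The device is always to be suspected, and *Not Related* needs a documented alternative cause. The distortion is therefore among the related grades. It does not move events out of them.
- An event graded too low still appears as *Potentially Related* in the relationship summary and in the individual listings, and in the separate listing if it is serious.
- Capture is intact. Section VI.3.4 sends every adverse event during the study to the sponsor whatever its grade. Reporting after the study covers any event considered related, not only the top grades.
- Several expected events, such as postoperative infection, pain and fever, have the operation as an obvious competing cause. They could be graded *Potentially Related* even with the condition removed.

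What does not stand is that clinical judgement settles the matter. If investigators grade above what the definition allows, the grade depends on whether the definition was followed. That is a reason to reconcile the text.

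**Conclusion.** The point holds as a defect in the grading definitions. For a screw left in place, a screw-caused event with no other likely cause cannot literally be *Probably Related*, is hard to grade *Definitely Related*, and fits *Potentially Related* poorly. The tendency is towards the lower related grade in the summaries by relationship. The protocol gives no expected event rate or grade distribution, so the size of the shift cannot be stated. It does not touch the co-primary endpoints or adverse-event capture during the study.

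A reader might infer more: that both top grades are out of reach for every expected event, so that a report of no definite or probable events would be an artefact of the definition. The documents do not support this. *Definitely Related* is worded more softly, the lead-in leaves room for judgement, and some expected events would sit lower in any case. The protocol also defines no combined definite-or-probable rate, threshold or success criterion, so an error bound on such a rate would describe a statistic the plan does not use.

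The conclusion assumes that the definitions are applied as written and that the screw is not removed.

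**What to change.** In VI.3.3.2, delete the dechallenge and rechallenge conditions from *Definitely Related* and *Probably Related*, or state that they apply only if the screw is removed. Base both grades on criteria an implant can meet, in line with the lead-in: plausible timing, evidence of a causal link, and exclusion of other causes (ruled out for the upper grade, unlikely for the lower). Carry the same wording into the eCRF guidance. In the same edit, align the name *Potentially Related* with the text beneath it, which calls the grade possibly related.

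A row pooling the definite, probable and potential grades in the summaries would be a useful addition, because it does not depend on where the line between the related grades falls. It is optional.

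The cost is a change to protocol and eCRF wording, with no change to visits or patient care. The downside is that the number of events graded probably or definitely related may rise slightly.

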	
Subjective IKDC:
 
The minimum relevant difference expected in the change at 7 months on the functional IKDC score is 11 points and the standard deviation expected in the IKDC score at both timepoint is 13 points. A total of 32 evaluable patients will be necessary to ensure a 90% power to detect a significant difference in the change at 7 months for two-sided test at the 5% level using paired Student t test or Wilcoxon test (depend of normality assumption).
 
Objective IKDC:
 
It is expected that 96% of patient will have modalities C or D before surgery [5]. Based on the investigator's experience, the proportion of total expected to shift from an IKDC modalities C or D to modalities A or B is 70% and proportion of total expected to shift from an IKDC modalities A or B to modalities C or D is 1%. A total of 11 evaluable patients will be necessary to ensure a 90% power to detect a significant difference for two-sided test at the 5% level using McNemar test.
 
In order to ensure sufficient statistical power for both comparisons, the larger of the two required sample size is planned to be included, i.e. 32 patients.
 
However, to increase the estimate precision of the co-primary endpoint, 50 completed patients will be targeted. With 50 patients, a precision around 13% can be achieved for the objective IKDC score and 3.6 points for the subjective IKDC score. This sample size will provide a final statistical power for primary objective of 97%.
 
Accounting for a maximum of 10% dropouts or missing data, 56 patients should be recruited in the study.

Duration of the research	
 - Duration of the inclusion period: 12 months - Follow-up period per participant: maximum 12 months (at most 4 months before surgery and 8 months of follow-up) - Total research duration: 24 months

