In the case of a new medical fact, the Sponsor, will be responsible for reporting new facts to the authorities in accordance with national regulations, as follows:

- Inform without delay the ANSM about the new medical fact, at the following email address: [contact] with the following subject: Fait nouveau / trial number/ international non-proprietary name (INN) or substance code and including:
 - ID-RCB N°,
 - Title of the study protocol,
 - Protocol code number,
 - Summary of the new fact and urgent safety measures implemented if necessary,
 - All relevant information for the evaluation of the new fact.
- Inform without delay the director of the Agence Régionale de Santé (ARS; regional health agency) and the Ethics Committee (CPP).

Any follow-up information with regards to the new safety medical fact will be reported to the regulatory authorities within 8 calendar days, and details regarding the urgent safety measures set up will be sent within 15 days to the regulatory authorities.

VII. STATISTICAL ASPECTS

VII.1. SAMPLE SIZE DETERMINATION

The sample size required for the study was determined in order to obtain sufficient final statistical power considering the 2 main criteria (co-primary endpoint). The statistical power used to determine the sample size required for each of the 2 main criteria is 90% to obtain a final statistical power of at least 80%.

Subjective IKDC:

The minimum relevant difference expected in the change at 7 months on the functional IKDC score is 11 points and the standard deviation expected in the IKDC score at pre-surgery and at 7 months is 13 points. A total of 32 evaluable patients will be necessary to ensure a 90% power to detect a significant difference in the change at 7 months for two-sided test at the 5% level using paired Student t test.

Objective IKDC:

It is expected that 96% of patient will have modalities C or D before surgery [5]. Based on the investigator's experience, the proportion of total expected to shift from an IKDC modalities C or D to modalities A or B is 70% and proportion of total expected to shift from an IKDC modalities A or B to modalities C or D is 1%. A total of 11 evaluable patients will be necessary to ensure a 90% power to detect a significant difference for two-sided test at the 5% level using McNemar test.

In order to ensure sufficient statistical power for both comparisons, the larger of the two required sample size is planned to be included, i.e. 32 patients.

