However, to increase the estimate precision of the co-primary endpoint, 50 completed patients will be targeted. With 50 patients, a precision around 13% can be achieved for the objective IKDC score and 3.6 points for the subjective IKDC score. This sample size will provide a final statistical power for primary objective of 97%.

Accounting for a maximum of 10% dropouts or missing data, 56 patients should be recruited in the study.

VII.2. ANALYSIS SETS

Four populations will be defined:

- Screened population will include all patients entering the study,
- Safety Set (SS) population will include all patients who received the surgical intervention,
- Full Analysis Set (FAS) population will be defined by all patient who received the CIS product and in whom at least one efficacy information has been collected after the application of the CIS,

- Per-Protocol (PP) efficacy population will include all patients in FAS population without any major protocol deviation.

Remark: according to the ICH E9 recommendations, this subset of patients corresponds to a subset of the full “intention-to-treat” analysis set, being the Full Analysis Set (FAS).

VII.3. MISSING VALUES AND DROP-OUT

For the primary analysis (FAS analysis), in the case of a patient with missing data, the corresponding data will not be replaced.

For sensitivity analyses, some of the missing data may be replaced. It will be performed according to the following scenarios:

- Best-worst scenario: the missing data on the pre-surgery objective IKDC score will be considered with an objective IKDC score to A and missing data on the 7-months objective IKDC score will be considered with an objective IKDC score to D.
- Worst-best scenario: the missing data on the pre-surgery objective IKDC score will be considered with an objective IKDC score to D and missing data on the 7-month objective IKDC score will be considered with an objective IKDC score to A.
- Last Observation Carry Forward (LOCF) method: the missing data on the 7-months subjective IKDC will be replaced using LOCF method.

No other missing data will be replaced.

VII.4. STATISTICAL ANALYSIS

VII.4.1. GENERAL CONSIDERATION

A Statistical Analysis Plan (SAP) will be written by the biostatistician detailing the statistical analysis. This document will be approved and signed by the Sponsor and the Coordinating Investigator before the first database lock.

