The statistical analysis will be performed on SAS® version 9.4 or later (or equivalent statistical software).

➤ Descriptive statistics

Quantitative variables will be described by the number of values entered, the number of missing data, the mean, the standard deviation, the 95% CIs for the means, the median, the 1st and 3rd quartiles, the minimum and maximum.

Qualitative variables will be described by the number of data filled in, the number of missing data, the frequency and the percentage of each modality. The 95% CIs of the percentages will be performed using exact confidence limits method.

All variable in the database will be described using descriptive statistics and all individual data will be presented in listings.

➤ *Inferential test*

All tests will be two-sided and the type I error (α) will be set at 5%.

Quantitative score at 7-months visit will be compared to the score before surgery using paired Student t test or Wilcoxon test (depend of normality assumption).

Qualitative score at 7-months visit will be compared to the score before surgery using McNemar test or Q Cochrane test (if expected sample size for the contingency cell are less than 4).

One interim analysis and no sub-group analysis will be planned.

➤ *Pre-analysis review of patient data*

Following the ICH guideline E9, a data review meeting will be held before the final database locking. The following items will be discussed:

- By-patient, list of protocol violations and other issues with the data, and definition of the analysis sets,
- Need for amendment to the SAP, based on newly gained research information and on the examination of the data.

If required, the SAP will be amended. Data discrepancies detected at the pre-analysis data review meeting will be resolved. Subsequently, the database will be locked, and the analyses will be performed.

➤ *Protocol deviations*

A protocol deviation is any noncompliance with the clinical trial protocol, International Conference on Harmonisation Good Clinical Practice (ICH GCP), or manufacturer recommendation requirements. As a result of deviations, corrective actions are to be developed by the site and implemented promptly. It is the responsibility of the site investigator to use continuous vigilance to identify deviations. All deviations must be reported in study source documents.

All protocol deviations will be listed before the data review meeting and reviewed during this meeting and classified as “minor” or “major”.

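### The 3.6-point precision for the subjective IKDC uses the single-visit SD of 13, whereas the 32-patient calculation needs an SD of change near 18.4; on that SD the margin is 5.1 points

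*Protocol*

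**What the plan says.** Section VII.1 sizes the subjective IKDC comparison from two inputs. The first is the effect: "The minimum relevant difference expected in the change at 7 months on the functional IKDC score is 11 points". The second is the spread: "the standard deviation expected in the IKDC score at pre-surgery and at 7 months is 13 points". From these it concludes: "A total of 32 evaluable patients will be necessary to ensure a 90% power to detect a significant difference in the change at 7 months", by a two-sided paired t test at 5%. It gives neither an SD of the change nor a pre/post correlation.

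The section then raises the target to 50 completed patients. Its only stated reason is better precision for the co-primary endpoint, and it supports this with: "With 50 patients, a precision around 13% can be achieved for the objective IKDC score and 3.6 points for the subjective IKDC score". It adds that 50 patients give 97% power for the primary objective. The Synopsis (Study size) carries the same figures.

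Section II.1 defines the primary comparison as the 7-month scores (V3) against the pre-surgery scores (V-1). Section VII.4.2 makes this within-patient comparison the criterion of success.

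**The concern.** The SD of a score at one visit and the SD of the within-patient change are different quantities, linked by the pre/post correlation. The 32-patient figure appears to rest on an SD of change larger than 13, while the 3.6-point precision appears to use 13 itself. If so, the same section uses two incompatible SDs for the same contrast, and the error margin quoted for the co-primary endpoint is that of a mean at one visit.

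This matters because power was already met at 32, so the case for 50 patients rests on precision. Section I.3 also hypothesises an improvement of at least 11 points. A reader will set the quoted margin against that threshold when judging how firmly the study can place the mean change.

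**Working it through.** **Inputs (section VII.1; the test level is also in VII.4.1).** Effect 11 points; SD 13 at each visit; two-sided 5%; power 90%; stated N = 32; target n = 50; stated precision 3.6 points.

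**1. Reproduce the 3.6.** The protocol does not define precision. Read as a 95% half-width, 1.96 × SD/√n:

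- 1.96 × 13/√50 = 3.60 (3.69 with the t quantile on 49 degrees of freedom).
- Working back, 3.6 × √50/1.96 = 12.99. Allowing for rounding (3.55 to 3.65), the SD lies between 12.8 and 13.2.

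So the SD used is 13, the single-visit value.

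**2. Reproduce the 32.** With equal SDs at the two visits and correlation ρ, the SD of change is 13 × √(2(1 − ρ)).

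- At ρ = 0 this is 13 × √2 = 18.38.
- Exact paired t test (noncentral t, n − 1 degrees of freedom, noncentrality 11√n/SD of change): power is 89.7% at n = 31 and 90.6% at n = 32, so N = 32, as stated.
- The normal approximation gives (18.38 × (1.960 + 1.282)/11)² = 29.35, rounded up to 30.
- The SDs of change that return exactly 32 run from about 18.28 to 18.59, which means a correlation of about zero.

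**3. Can one SD of change give both figures?** If the SD of change were 13 (ρ = 0.5), 3.6 would be right for the change, but the exact calculation would then need 17 patients. By assumed correlation:

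| ρ | SD of change | N for 90% power | Half-width at n = 50 |
|---|---|---|---|
| 0 | 18.38 | 32 | 5.10 |
| 0.2 | 16.44 | 26 | 4.56 |
| 0.3 | 15.38 | 23 | 4.26 |
| 0.5 | 13.00 | 17 | 3.60 |
| 0.7 | 10.07 | 11 | 2.79 |

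No row contains both 32 and 3.6.

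**4. Precision consistent with the 32.** 1.96 × 18.38/√50 = 5.10 points (5.22 with the t quantile). Over the whole range of SDs that return 32, it is 5.07 to 5.15. The ratio 3.6/5.10 is 0.71, so the stated figure is about 29% too low; equivalently, the consistent margin is about 42% wider.

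**5. Cross-check on power at n = 50.** With SD of change 18.38 the paired t test has 98.6% power. The McNemar test, with the protocol's 70% and 1% shifts, has more than 99.9%. The product is 98.6%, close to the stated 97%. With an SD of change of 13, power would exceed 99.99%. The stated power therefore also points to an SD of change near 18.4, and the 3.6 is the figure that does not fit.

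**The case against.** The best defence is that 3.6 is correct for what the sentence literally names. It speaks of the subjective IKDC score, and 13 is given as the SD of that score. Where the section means the change, it says so. The descriptive statistics in section VII.4.1 include 95% confidence intervals for means, so the half-width of a mean score is something the study will report. On this reading the quantity is merely unlabelled.

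That reading does not hold. The sentence follows directly on the statement that 50 patients are targeted for the precision of the co-primary endpoint, which sections II.1 and VII.4.2 judge on the within-patient comparison. Nothing marks 3.6 as a one-visit margin. Even as one, it suits only the post-operative mean: section I.2 justifies 13 for the post-operative state, and the pre-operative SDs in its table are 14.2, 17.1 and 18.1.

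Three parts of the objection do stand:

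- The companion figure for the objective IKDC does not settle what was meant. The proportion shifting from C or D to A or B gives 1.96 × √(0.7 × 0.3/50) = 12.7%, but the paired difference and the 7-month proportion also come out around 13%.
- The 5.1 depends on the zero correlation implied by N = 32. Among non-negative correlations it is the widest margin, and a positive correlation would narrow it.
- The consequence is limited. No success criterion uses the 3.6, and going from 32 to 50 patients still improves precision: on the SD of 18.38, from 1.96 × 18.38/√32 = 6.4 points to 5.1.

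**Conclusion.** The concern holds. The stated precision and the stated sample size rest on different SDs, and 3.6 points is not the error margin of the primary contrast on the SD that yields 32 patients. On that SD the margin is 5.1 points (5.2 with the t quantile). This assumes that precision means a 95% half-width, that the SD is 13 at both visits as stated, and that the correlation is the zero value implied by N = 32. If the true correlation is positive, the margin will be smaller and reaches 3.6 at 0.5, but the protocol states no such value and adopting one would change the 32.

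This is a wrong stated figure, not a design flaw. The 32, 50 and 56 patients, the planned tests and the power all stand, and 5.1 points remains well below the 11-point threshold.

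**What to change.** In section VII.1 and in the Synopsis (Study size), state the SD of change used for the 32 patients (18.4, from 13 at each visit with zero correlation) and give the precision of the mean change with 50 patients as about 5.1 points (5.2 with the t quantile).

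Alternatively, state and justify a pre/post correlation and recompute from it the 32, the precision and the 97% power together.

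If the authors wish to keep 3.6, it should be labelled as the half-width of a mean at a single visit, with the figure for the change given beside it.

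The cost is wording only. With the first or third option, enrolment and analysis stay as they are, and the margin reported for the primary contrast becomes less favourable. With the second, the minimum of 32 would fall for any material positive correlation, while the target of 50, set for precision, need not move.
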